11.2 Analysis

Population: Table: ITT
Listing: ITT

Statistics: Overall treatment exposure and compliance to study medication will be summarized by using continuous measures (number of participants, mean, SD, median, minimum & maximum) and Overall compliance categorized by count and percentage.

The visit wise compliance counts will be presented for Visit 3, Visit 5 and End of Treatment.

The listing will be presented by participant number.

12. Medical and treatment history

12.1 Variables and derivations

Medical history will be coded using the MedDRA central coding dictionary Version 26.0 or higher.

The following parameters will be summarised for the participant's medical history:

- Number of participants with at least one medical history
- Number of participants for each medical history by SOC and PT

12.2 Analysis

Population: Table: ITT

Listing: ITT

Statistics: Medical history will be summarised by SOC and PT (frequency and percentages) for table and listing also be presented.

13. Prior, concomitant, and other medications

13.1 Variables and derivations

All medications will be coded using the WHO-DD, dated March, 1, 2023 or higher.

Prior medications are defined as any medication taken prior to first administration of the study treatment.

'Concomitant medications' are defined as any medication taken after or on the day of first administration of the study treatment.

In section 22 Appendix 2 the algorithm is given for calculation of partial date imputation for prior and concomitant medications, and it will be used for partially missing prior and concomitant medications, start and end date imputation.

The following parameters will be summarised as prior and concomitant medications separately:

- Number of participants with at least one prior and concomitant medication
- Number of participants for each prior and concomitant medication by ATC and PT.

13.2 Analysis

Population: Table: ITT

Listing: ITT

Statistics: Prior and concomitant medication will be summarised by ATC and PT (frequency and percentages) for table and listing also be presented.

14. Adverse events

14.1 Variables and derivations

Adverse Events (AEs) will be coded using standard GSK dictionary, MedDRA central coding dictionary, version 26.0 or higher.

For the definition of Adverse events (AE) and Serious adverse event (SAE) refer to the protocol section 10.6.

The following parameters will be summarised for the participant's adverse events as mentioned in eCRF:

- Number of participants with at least one AEs pre treatment
- Number of participants with at least one AE during treatment
- Number of participants with at least one AE post treatment
- Number of participants with at least one Drug related AE.
- Number of participants with at least one serious AEs
- Number of participants with at least one Drug related serious AEs
- Number of participants with at least one AESI
- All Adverse Events
- Ongoing AEs
- AEs by Severity
- AEs by Outcome
- AEs by Action Taken with Study treatment
- AEs leading to Death

Derivations:

- The question "Adverse event related to study treatment" is answered "Yes," then respective AEs will be considered as treatment related AE.
- The question "Is the adverse event serious" is answered as "Yes" then respective AE will be considered as serious AEs.
- The question "Is the adverse event serious" is answered as "Yes" and the question "Adverse event related to study treatment" is answered "Yes," then respective AEs will be considered as treatment related SAEs.
- If seriousness criteria are "DEATH" and outcome of adverse event is "FATAL" then we will consider it as AE leading to death.
- Participant's primary reason for discontinuation captured in the eCRF page, study treatment discontinuation is "ADVERSE EVENT" then we will consider it as AE leading to early withdrawal from study.
- Pre- Treatment AEs: AE Start Date < Study Treatment Start Date
- Post- Treatment AE's: AE Start Date > Study Treatment Stop Date

- During Treatment AE's: Treatment Start Date \leq AE Start Date \geq Treatment Stop Date

In section 22 Appendix 2 the algorithm is given for calculation of partial date imputation for Adverse Events, and it will be used for partially missing AE, start and end date imputation.

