Participants who have consented meet all the eligibility criteria and who have successfully completed all protocol procedures at screening will receive the following study intervention for 12 weeks:

FF/UMEC/VI 100mcg/62.5mcg/25mcg via the ELLIPTA inhaler once daily in the morning

On the morning of study clinic Visit 2 (start of treatment), Day 28 (Visit 3) and telephonic contact Day 84 (telephonic Visit 4), participants will refrain from taking their morning dose of study intervention/COPD medication until instructed to do so by clinic personnel. Participants will take their last dose of study treatment on Day 84 and will return for their final clinical assessments on Day 85 (Visit 5). A safety follow-up (Visit 6) will be conducted by phone call approximately one week later. Participants may continue their study-supplied rescue salbutamol from the start of the study treatment phase until the end of the treatment period.

A participant will be considered to have completed the study when they have completed all phases of the study including screening, the treatment phase, and safety follow-up.

[figure not shown]
The total duration of participant participation will be approximately 13 weeks, 12-week treatment period and a 1-week follow-up period.

Participants that permanently discontinue study intervention are not required to withdraw from the study. If for any reason a participant must permanently discontinue study

treatment, every effort should be made by the investigator/staff to keep the participant in the study. However, a participant may voluntarily withdraw from participation in this study at any time. The investigator may also, at his or her discretion, withdraw a participant from further study participation. Participants who are withdrawn from the study will not be replaced.

Data Monitoring/ Other Committee: No

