7. DISCONTINUATION OF FF/UMEC/VI AND PARTICIPANT DISCONTINUATION/WITHDRAWAL

7.1. Discontinuation of FF/UMEC/VI

Participants have the right to discontinue FF/UMEC/VI before the end of the study. A participant may also be asked to discontinue FF/UMEC/VI at the Investigator's discretion.

Participants that permanently stop FF/UMEC/VI should return to the clinic as soon as possible, in order to complete the Treatment Discontinuation visit. The evaluations and procedures to be completed are outlined in the SoA (Section 1.3)

Participants that discontinue FF/UMEC/VI are encouraged to remain in the study and every effort should be made by the Investigator/staff to keep the participant in the study, to collect important efficacy and safety data.

If possible, participants should return to the clinic to complete all scheduled visits. If this isn't possible, visits should be completed by telephone. Ideally, participants should return to the clinic to complete Visit 5, to collect important spirometry data, however, if this isn't possible, this visit could be completed by telephone. A safety follow-up phone call (Visit 6) should also be conducted 7 days after Visit 5.

Following discontinuation of study intervention, if participants are unwilling to return to the clinic for their scheduled visits, the Investigator/site staff should contact the participant by telephone at the protocol designated visit time intervals to collect the following:

- SAEs
- AEs assessed as related to study participation
- AEs resulting in discontinuation of study intervention or withdrawal from the study
- COPD exacerbations
- Concomitant medication
- A safety follow-up phone call (Visit 6) should also be conducted 7 days after Visit 5.

A participant may be withdrawn from study intervention at any time. A reason for premature discontinuation of study intervention (e.g., AE, lack of efficacy, protocol deviation, Investigator discretion, consent withdrawn etc.) must be captured in the eCRF.

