7.1.4. COVID-19 stopping criteria

All participants suspected to have contracted COVID-19 must be tested using a molecular (PCR or antigen test) approved by the regulatory authorities in India.

Participants that test positive for COVID-19 must immediately discontinue study intervention and complete the Study Treatment Discontinuation Visit. Participants are encouraged to remain in the study and every effort should be made by the Investigator/staff to keep the participant in the study.

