9.1 Variables and derivations

End of trial classifications are defined as follows:

- Screening failure:

Participants who consent to participate in the clinical study but are not subsequently entered in the study & do not meet the criteria for participation in the study.

- Completed trial:

All participants who completed the trial, as indicated in the end of study: Trial Disposition page of eCRF form, will be assumed to have completed trial.

- Lost to follow-up:

A participant will be considered lost to follow-up if he or she repeatedly fails to return for scheduled visits and is unable to be contacted by the study site. Site personnel or designee are expected to make diligent attempts to contact participants who fail to return for a scheduled visit or were otherwise unable to be followed up by the site.

The following parameters will be summarized for the Participant's disposition table as per eCRF:

- Number of screened participants
- Screening status
 - Entered into trial
 - Failed
- Screen failure reasons
- Number of participants in screened population
- Number of participants in enrolled population
- Number of participants in Intent-to-Treat population
- Number of treatment completed participants
- Number of study ongoing participants
- Number of treatment discontinued participants
- Reason of treatment discontinued participants
- Number of study completed participants
- Number of study withdrawn participants
- Reason of study withdrawn

Note- Subjects may have only one primary reason.

Participants who completed the study, as indicated on the “End of Study: Trial Disposition” form of the (eCRF), will be assumed to have completed the study. And participants who completed the treatment, as indicated on the “Study Treatment Discontinuation: Treatment Discontinuation” form of the (eCRF), will be assumed to have completed the treatment. (i.e., participants who completed the trial will be counted under both the “completed treatment” and “completed trial” category).

The following parameters will be summarized for the study discontinuation table as per eCRF Participant's primary reason for discontinuation (reasons mentioned in eCRF end of study form) which is as follows:

- Adverse event
- Death
- Lost to follow-up
- Pregnancy
- Protocol violation
- Screen failure
- Consent withdrawal not due to an adverse event
- Study terminated by sponsor
- Migration from the study site such that follow up visits are not possible
- Other

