14.2 Analysis

Population: Table: ITT

Listing: ITT

Statistics: An overall summary will be presented as the number of participants within each of the event type categories described in the above section, including the incidence of AEs by preferred term (PT) and System organ class (SOC) sorted by decreasing frequency within the SOC & PT. Number and proportion of participants with AEs will be presented. Both number of participants, number of event (One participant may be counted more than once) and percentage will be provided.

The summary of drug related adverse events, serious adverse events, serious drug related adverse events, Adverse Events Leading to Permanent Discontinuation of Study Treatment or Withdrawal from Study and Adverse events of Special interest will be presented by SOC and PT also summary of drug-related AEs by SOC, PT and maximum intensity will be provided.

The most common reported ($\geq 3\%$) AEs and SAEs will be summarized by overall frequency. The Adverse Event will be summarized and presented in data listings using ITT population with all AEs (including coding details SOC and PT only) and participants with SAEs, AESIs, Fatal AEs and events resulting in study discontinuation will be listed separately by participant's number.

Note: If there are uncoded adverse events, then the uncoded category will be added in the AEs by SOC/PT summary tables.

15. Vital Signs

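### SAP 14.1 derives AE-driven withdrawal from the study from the treatment-discontinuation page, so it labels some participants wrongly, can miss others, and identifies no AE record

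*SAP*

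**What the plan says.** The rule is among the derivations in SAP 14.1. Its condition is that the "Participant's primary reason for discontinuation captured in the eCRF page, study treatment discontinuation is" adverse event; its consequence is "then we will consider it as AE leading to early withdrawal from study". No other rule in the SAP defines this category.

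SAP 14.2 plans a summary by SOC and PT of "Adverse Events Leading to Permanent Discontinuation of Study Treatment or Withdrawal from Study", and a separate listing by participant of the events that ended study participation. Protocol 8.2 also promises a summary of AEs leading to withdrawal.

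The protocol separates the two outcomes. Synopsis (1.1): "Participants that permanently discontinue study intervention are not required to withdraw from the study". Section 7.1: "Participants that discontinue FF/UMEC/VI are encouraged to remain in the study". The same section, on what to collect by telephone from those unwilling to return, names the two as alternatives: "AEs resulting in discontinuation of study intervention or withdrawal from the study".

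SAP 9.1 also separates them. It counts treatment discontinuations and study withdrawals on different lines. It takes the study-discontinuation reasons from another source ("reasons mentioned in eCRF end of study form"), and adverse event is one of those reasons.

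**The concern.** The source field and the label describe different outcomes. The field records why treatment stopped; the label says the participant left the study. In this protocol the first does not imply the second.

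The level of the data does not match either. The primary reason is one value per participant, whereas the table by SOC and PT and the listing both need particular AE records. The neighbouring rules in SAP 14.1 for related, serious and fatal AEs all read fields of the AE record. This one does not, and it states no link to one.

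Safety is the primary objective, and AEs that end treatment or participation are a standard part of a safety report. At stake is whether that output names the right outcome and the right event, and whether it agrees with the disposition table.

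**Working it through.** **Step 1: apply the rule to the possible cases.**

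| Case | Result of the SAP 14.1 rule | Correct result for study withdrawal |
|---|---|---|
| Stops treatment for an AE and leaves the study for it | Flagged | Flagged |
| Stops treatment for an AE and stays to follow-up | Flagged | Not flagged |
| Stops treatment for another reason, later leaves the study because of an AE | Not flagged | Flagged |
| Completes treatment, leaves during the one-week follow-up because of an AE | Not flagged | Flagged |

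The rule is right in the first row only. The second row is the course that the protocol encourages. COVID-19 makes it foreseeable. Protocol 7.1.4 says "Participants that test positive for COVID-19 must immediately discontinue study intervention and complete the Study Treatment Discontinuation Visit" and then asks sites to keep the participant in the study. Protocol 8.2 has COVID-19 reported as an AE. If the site enters adverse event as the reason for stopping, the rule records a study withdrawal.

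**Step 2: identify the event.** Even in the first row, the rule selects a participant and not an AE. If that participant has several AEs, the SAP does not say which enters the table. SAP 14.1 separately plans a summary of AEs by action taken with study treatment, so an event-level field appears to exist. The rule does not use it.

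**Step 3: see where the wrong label lands.** The category is not among the 13 summary parameters listed in SAP 14.1. The SOC/PT table in SAP 14.2 covers treatment stops and study withdrawals together, so a treatment stop is in place there. What remains is the separate listing of events that ended study participation. The missing event link affects both table and listing.

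**Step 4: size.** Inputs from Protocol 9.2: 220 evaluable, 229 enrolled, 4% withdrawal from study treatment.
- The plan's own figure: 220 / (1 − 0.04) = 229.2; stated 229.
- Treatment stops from all causes: 229 × 0.04 = 9.16, about 9.
- Share due to AEs: not given. Assumed range 25% to 100%: 9 × 0.25 = 2.25 up to 9 × 1 = 9, that is 2.25 / 229 = 1.0% to 9 / 229 = 3.9% of participants flagged.
- True study withdrawals among those flagged: also not given. The range runs from 0 if all stay to all of them if none stay.

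**The case against.** Much can be said for the plan as it stands.

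- **The combined table.** A reader might infer that the SOC/PT table itself misreports treatment stops. It does not, because its title covers both outcomes.
- **Missed withdrawals.** A reader might infer that AE-driven withdrawals are missed in general. Protocol 7.2 says that a participant who leaves the study stops study treatment at the same time, and Protocol 7.1 requires a recorded reason for stopping early. Most on-treatment AE withdrawals should therefore also appear on the treatment page. The gap is limited to withdrawal after treatment has ended, withdrawal after an earlier stop for another reason, and cases where the two forms give different reasons.
- **Other outputs.** SAP 9.1 summarises study-withdrawal reasons, including adverse event, apart from treatment discontinuation. All AEs are listed, and SAP 21.4.1 puts every eCRF variable with data into listings. A careful reader could often recover the truth.
- **Unrelated events.** A reader might infer that every AE of a flagged participant will be tabulated, multiplying the preferred terms. The SAP does not say so, and the documents give no number of AEs per participant. The eCRF may hold a link, and the output templates are a separate document (SAP 8). Neither is available here.

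These arguments narrow the consequences, and all of them stand. They do not rescue the rule. Followed exactly, it still gives a wrong label to anyone who stops for an AE and stays, and it still names no event for outputs that need one. That other outputs allow a correction is no reason to leave a wrong derivation in place.

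**Conclusion.** The rule is wrong as written, with limited consequences. It labels an AE-driven treatment stop as a study withdrawal, chiefly in the SAP 14.2 listing. It can miss an AE-driven withdrawal recorded only on the end-of-study form, and it does not identify the AE.

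About 9 participants is a ceiling on the mislabelling at the planned 4%, because that rate covers all causes of stopping and the rule selects only adverse event. The number with a wrong label could be zero. It depends on the AE share and on how many stay, neither of which the documents give. Participants who complete treatment and then leave during follow-up because of an AE fall outside that 4%; the documents give no figure for them.

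A reader might infer that the primary safety result is affected. It is not: the AE, SAE and AESI incidence in SAP 17 does not use this flag. The sample size is untouched, and the trial has no hypothesis test.

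**What to change.** Replace the single rule in SAP 14.1 with two.

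1. AE leading to permanent discontinuation of study treatment: derive per event, from the AE record's action-taken field.
2. AE leading to withdrawal from the study: derive from the end-of-study reason adverse event, matched to an AE record. If the eCRF has no direct link, state the matching rule.

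Show the two as separate rows within the existing SAP 14.2 table and listing, and check the counts against the disposition table in SAP 9.1.

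The cost is a SAP revision, a change of source variable and small changes to two outputs. The first flag should need no new data, provided the action-taken field has a code for permanent discontinuation. Whether the second needs more than a written matching rule depends on the eCRF, which the documents do not show.

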11.1 Variables and derivations

The date of first study treatment administration will be derived as the first date of dosing from the treatment administration eCRF page. The date of last study treatment administration will be derived as the date of last dose of study treatment from the treatment administration eCRF page. If this date is not available, then the date of last administration will be derived as the last date of dosing from the treatment administration eCRF page.

Interruptions, compliance, and dose changes will not be considered for calculating the duration of exposure, which will be derived as follows:

- $$\text{Duration of exposure (days)} = (\text{Date of last study treatment administration} - \text{Date of first study treatment administration}) + 1$$

Treatment compliance:

Treatment compliance will be assessed for the entire treatment period, as well as at visits 3 and 5.

If a dose counter start count is missing, then it will be assumed to be 30 for the ELLIPTA DPI. If any dose counter stop is missing, then the number of doses taken will be set to missing for that inhaler.

Number of doses of study drug taken by each participant from each inhaler = Dose counter start value – dose counter stop value.

The derivation for treatment compliance during the treatment period is defined as the sum of (dose counter start value – dose counter stop value) over all inhalers dispensed to the participant and returned during the treatment period (i.e., from study Treatment administration to EOS/EW visit) and percentage compliance will be calculated as follows:

- $$\text{Treatment compliance (\%)} = \frac{\text{Total number of doses received}}{\text{Duration of exposure (days)}} \times 100$$

Overall compliance will be categorized as follows:

- < 50 %
- $\geq 50\%$ to < 80%
- $\geq 80\%$ to < 95 %
- $\geq 95\%$ to $\leq 105\%$
- $> 105\%$ to $\leq 120\%$
- $> 120\%$

If a participant receives a treatment other than the scheduled treatment during the study, the compliance will still be calculated using data from all containers received and overall exposure start and stop dates.

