16.2 Analysis

Population: Table: ITT

Listing: ITT

Statistics: The physical examination & oropharyngeal assessment will be presented in data listings and summarised as number and percentage (n and %) at all assessment timepoints. Physical & oropharyngeal examination data will be classified as normal & abnormal.

17. Primary Estimand

17.1 Incidence of adverse events (AE), serious adverse events (SAE) and adverse events of special interest (AESIs) during 12 weeks.

As per the protocol, estimand will be defined as follows:

- **Summary measure:** Number and percentage of participants experiencing an AEs, SAEs and number and percentage of participants experiencing AESIs by system organ class and by preferred term.
- **Population of interest:** COPD patients in India.
- **Key intercurrent events (ICEs):** Discontinuation of treatment (for any reason).
- **Strategy for intercurrent events:** A while on treatment strategy will be used for treatment discontinuation. This estimates the percentage of participants experiencing an AE or SAE while taking treatment. Participants that test positive for COVID-19 will immediately discontinue study treatment. Therefore COVID-19 will be included as the intercurrent event of study treatment discontinuation and will be handled with while on treatment strategy for the primary estimand.
- **Supplementary Estimand:** Incidence of adverse events (AE), serious adverse events (SAE) and adverse events of special interest (AESIs).
- A supplementary estimand will be defined using identical properties as for the primary estimand (summary measure, population of interest and key intercurrent events), however this supplementary estimand will report all AEs regardless of the discontinuation of study treatment.
- **Strategy for intercurrent events:** Treatment policy strategy will be used for treatment discontinuation. This summary will therefore be inclusive of all on-treatment and post-treatment AEs.

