17.1.2 Primary estimand analyses

Population: Table: ITT

Listing: NA

Statistics:

While on-treatment Policy: Values of the variable up to the time of the intercurrent event.

This strategy summarises the variable while the patient actually receives their randomised treatment. An example of use of this strategy is the standard approach to safety data. Adverse events in efficacy trials are usually summarised over the period while a subject is receiving the randomised treatment.

The primary estimand analysis will be performed for participants experiencing an AE, AESI & SAE while taking treatment. It will follow while on treatment policy. But if a subject discontinues treatment during this period of Visit 2-Visit 4 then values only before discontinuation point will be considered.

Treatment Policy: Actual values of the variable regardless of whether the intercurrent event has occurred.

This approach requires collection of data after the intercurrent event of interest (e.g. continued collection if a patient discontinues treatment) and corresponds to a full ITT approach. If the patient also withdraws from the study, then this becomes a missing data problem. The supplementary estimand analysis will be performed for participants experiencing AE, AESI & SAE while taking treatment and post treatment. It will follow treatment policy.

Summary will be presented as the number of participants experiencing AE, AESI & SAE including the incidence of AEs by alphabetically preferred term (PT) sorted by decreasing frequency within the system organ class (SOC). Number and proportion of participants with AEs will be presented. Both number of participants, number of event (One participant may be counted more than once) and percentage will be provided.

Note: If there are uncoded adverse events, then the uncoded category will be added in the AEs by SOC/PT summary tables.

For the supplementary analysis refer to the SAP section 14.

18. Secondary efficacy estimands

18.1 Change from baseline in trough FEV1 on Day 85 and Day 28

As per the protocol, estimand will be defined as follows:

- **Summary measure:** Mean change from baseline in trough FEV1 on Day 85.
Mean change from baseline in trough FEV1 on Day 28.
- **Population of interest:** COPD patients in India.
- **Key intercurrent events (ICEs):** Discontinuation of treatment.

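### Does the SAP need one stated end date, or a one-day lag, for on-treatment adverse events?

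*SAP*

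**What the plan says.** SAP 14.1 sorts adverse events by start date into pre-treatment, during treatment and post-treatment. The last category is "Post- Treatment AE's: AE Start Date > Study Treatment Stop Date". The second inequality in the During Treatment line is printed the wrong way round. That slip is a separate matter; here the line is read as start date ≤ onset ≤ stop date.

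SAP 11.1 supplies a stop date for exposure: "The date of last study treatment administration will be derived as the date of last dose of study treatment". SAP 14.1 does not say that its stop date is this variable.

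SAP 17.1.2 describes the while-on-treatment strategy as "Values of the variable up to the time of the intercurrent event" and then adds: "But if a subject discontinues treatment during this period of Visit 2-Visit 4 then values only before discontinuation point will be considered". Its only pointer to the classification is "For the supplementary analysis refer to the SAP section 14". The heading of SAP 17.1 limits the primary endpoint to "adverse events of special interest (AESIs) during 12 weeks".

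The protocol synopsis states: "Participants will take their last dose of study treatment on Day 84 and will return for their final clinical assessments on Day 85". The Schedule of Activities places Visit 5 (Day 85) under the Treatment header, and its footnote e mentions a Day 85 dose.

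**The concern.** The incidence of adverse events is the primary endpoint, and the plan appears to give several end points for the period in which events count. An event starting the day after the last dose is post-treatment under SAP 14.1, although Visit 5 sits under Treatment in the schedule and trough FEV1 is measured that day as a treatment effect. For someone who stops early, the two phrases in SAP 17.1.2 differ on whether the boundary day counts, and the discontinuation point could be the last-dose date or a later decision date. Two programmers could then report different counts for the same data. The suggested remedy was one end-date rule with a one-day extension after the last dose.

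**Working it through.** **1. Completers.** Take first dose on Day 1, last dose on Day 84 (protocol synopsis) and follow-up to Day 92.

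| Source | Last day counted | Onset on Day 85 |
|---|---|---|
| SAP 14.1, inequality read as intended | Day 84 | out |
| SAP 17.1.2, Visit 2 to Visit 4 | Visit 4, nominally Day 84 | out |
| SAP 17.1 heading, 12 weeks = 12 × 7 days | Day 84 | out |

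Visit 4 is the telephone contact at which the last planned dose is instructed, so its date follows that dose even when it moves within the Day 80 to 86 window. The sources agree for the 220 of 229 participants expected to complete. If a Day 85 dose is recorded, as footnote e allows, the stop date under SAP 14.1 becomes Day 85 and a Day 85 onset is counted. In either case that rule follows the recorded last dose. The synopsis and footnote e must be reconciled on their own account.

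**2. Discontinuers.** The expected number is 229 × 0.04 = 9.2, about 9.

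- If the discontinuation point is the last-dose date, an onset on that day is in under SAP 14.1 and out under the strictly-before wording of SAP 17.1.2.
- If it is a later decision date, an onset on the day after the last dose can be out under SAP 14.1 and in under SAP 17.1.2.

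The difference is real, but it concerns onsets around the boundary only.

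**3. The plan's own figure.** Protocol Table 5 gives 0.8904 as the chance of at least one event at a risk of 0.01 with 220 participants. The check is 1 − 0.99^220 = 0.8904. With a constant hazard, ending the window on Day 83 or Day 85 instead of Day 84 gives 0.8875 or 0.8933. The sample-size statement barely depends on the boundary.

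**4. Size of one extra day in completers.** The documents give no overall adverse event rate, so 12-week risks p of 5%, 20% and 50% are assumed, with events evenly spread.

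- Daily hazard: h = −ln(1 − p)/84.
- Expected first events on Day 85: 220 × (1 − p) × (1 − e^(−h)).
- 95% half-width of the incidence: 1.96 × √(p(1 − p)/229).

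| p | First events on Day 85 | Points of 229 | Half-width, points |
|---|---|---|---|
| 5% | 0.128 | 0.06 | 2.82 |
| 20% | 0.467 | 0.20 | 5.18 |
| 50% | 0.904 | 0.39 | 6.48 |

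**5. Size of the boundary day in discontinuers.** Expected onsets on the last-dose day are 9 × (1 − e^(−h)) = 0.0055, 0.024 and 0.074 of a participant. These are onsets of any event, so they overstate the change in the proportion with at least one event. Even spread may fail here, because events can cause stopping. Each participant moved is 1/229 = 0.44 points. The ceiling is all 9 moved, 9/229 = 3.9 points. That would require every discontinuer to have a first event exactly on the boundary.

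**6. Where a reclassified event goes.** It stays in the post-treatment counts of SAP 14.1 and in the treatment-policy summary. If it led to stopping, it also appears in the SAP 14.2 table of "Adverse Events Leading to Permanent Discontinuation of Study Treatment or Withdrawal from Study", which states no on-treatment restriction.

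**The case for a change.** The strongest case for a change is reproducibility. A primary endpoint should have one flag, named once. SAP 17.1.2 does not say that the SAP 14.1 categories select the primary-estimand events, and correcting the reversed inequality alone would not settle the discontinuer boundary. Physical, vital-sign and oropharyngeal examinations after screening occur only at Visit 5 or the discontinuation visit, so a finding dated at detection could carry a Day 85 onset. The clarification would be cheap.

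The looseness for discontinuers stands: the two phrases do differ, and the reference date is not named. A programmer who builds the while-on-treatment table will nevertheless need a stop date, and SAP 11.1 has already derived one.

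The case for the extra day does not stand. No passage prescribes a lag, and ending at the last dose is the direct reading of an estimand defined by being on drug for 12 weeks. The Treatment header in the schedule also covers the discontinuation visit, which by definition follows stopping, so the header groups visits and does not define exposure. One day would not capture findings from a visit held two or more days after the last dose either. Visit 5 has its own window of Day 81 to 87, and the discontinuation visit has no fixed day. The number of findings first dated at such a visit cannot be estimated from the documents.

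**Conclusion.** No change follows. For completers the SAP's statements agree on an end at the last dose, and a one-day extension would be a different convention on which reasonable statisticians disagree. For about 9 expected discontinuers there is a small gap in wording, which an analyst would fill with the last-dose date of SAP 11.1.

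Under evenly spread events and a 12-week risk of 5% to 50%, the extra day is worth less than one participant: 0.06 to 0.39 points, against a half-width of 2.8 to 6.5. The boundary day in discontinuers is worth at most 0.074 of a participant under the same assumption. If events cluster at stopping, the effect could be larger, with an implausible ceiling of 3.9 points. No hypothesis is tested, and every event is still reported in another planned summary. The conclusion assumes that the SAP 14.1 inequality is read as intended and that the stop date is the last-dose date.
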